- Ocular Surface Disease Index (OSDI);^{49,50} a score of ≥13 out of 100 indicates dry eye
 - Subjects will be asked to fill out the questionnaires prior to reporting for the study. The questionnaires will not be scored until after data capture was completed on the subject.
- Tear meniscus height (OD/OS): Measured using Oculus Keratograph 5M: cursor measurement of three lower meniscus heights at approximately 7:00, 6:00 and 5:00
- Tear osmolarity using the Tear Lab method

- Slit Lamp Examination of the health of anterior structures (OD/OS):
 - Upper and lower lids and lashes assessed utilizing white light, diffuse beam (14 mm round), low illumination and 10x magnification
 - Bulbar and palpebral conjunctiva were then assessed using the same settings as those used for lids
 - Corneal health will be assessed utilizing white light parallel parallelepiped beam (~2mm wide, 14 mm tall) at a medium illumination and 16x magnification.
- Eyelid sign grading (OD/OS): Each of the following signs was given a grade of 0 (absent) or 1 (present). A grade of 1 was given if a feature had 2 or more appearances along the lid margin for that eye: ⁵¹⁻⁵³
 - Orifice metaplasia.
 - Orifice metaplasia: Clear-white filamentous shafts at the gland orifice, evident on direct illumination.
 - Vascularity/ brush marks.
 - Telangiectasia coming from palpebral conjunctiva.
 - Plugged or capped orifices (present if more than one caps on a given eyelid).
 - Ridging between orifices.
 - Eyelid margin irregularity.
 - Notching, ridging at the posterior lid margin border. [these two are equivalent]
 - Anterior or posterior orifice displacement.

- Tear Break Up Time (TBUT) with fluorescein staining (OD/OS): Detailed procedure description below.
- Corneal staining with sodium fluorescein (OD/OS)
- Staining was assessed as per the NEI (Score of 0-15) and OSS (screening and baseline only) schemes for each eye;⁵⁴⁻⁵⁶ detailed procedure description below.
- Conjunctival Staining with lissamine green (OD/OS):
- Staining was assessed as per the NEI (Score of 0-18) and OSS(Score of 0-12) schemes for each eye; ⁵⁴⁻⁵⁶ detailed procedure description below.
- Secretion Quality (OD/OS):
- Meibomian gland secretion quality will be assessed according to the Bron scale^{6,57} utilizing a Meibomian Gland Evaluator (MGE)⁵⁸ in order to standardize pressure applied and therefore values measured (gentle rather than a forceful expression);detailed procedure below.
- Schirmer I test, without anesthetic (OD/OS); detailed procedure below.
- Meibography using LipiView II (OD/OS) or K5M keratograpy); detailed procedure below.

Dry eye classification

Data from Procedure II will be analyzed, and each subject will be classified as moderate or severe ADDE or EDE-related to MGD; detailed classification scheme follows.

Detailed Description of Selected Tests

Fluorescein Tear Break-Up Time (TBUT)

- 6. Liquid sodium fluorescein (NaFl) will be used to visualize the breakup time. The dye will be sourced from Greenpark compounding pharmacy (Houston TX, USA) in 4 ml "droptainers" for study use. An amount of 2.0 µl of 1.0% wt./vol preservative-free NaFl was instilled using sterile pipette tips and a calibrated micropipette. The NaFl dye was stored at 4°C when not in use. Once opened, each bottle of dye was labeled with the date of opening and discarded after 28 days. The slit lamp biomicroscope was utilized to visualize the cornea with high illumination of cobalt blue light, wide beam (~14mm round), and 16x magnification. A yellow #12, 55mm Tiffen filter was held in front of the slit lamp optics to enhance observation of TBUT. A hand-held stopwatch was used to measure TBUT to the nearest 1/10th of a second.
- 7. The examiner has the subjects tilt their head back and look inferiorly while the examiner lifted the right upper eyelid to instill 2.0 µl of 1.0% wt./vol. preservative-free NaFl dye onto the superior bulbar conjunctiva of the right eye, and the process was repeated for the left eye.⁵⁵ The subject was then asked to position their head on the patient side of the slit lamp, and close their eyes until the examiner was ready to take a measurement, which took between 45-60 seconds. If there appeared to be inadequate fluorescein in the eye due to rapid drainage or excessive tearing from the subject such that tear break up time could not be measured, the investigator instilled an additional 2.0 µl of 1.0% wt./vol. preservative-free NaFl via pipette and documented on the chart that re-instillation was necessary. The amount of

fluorescein even with re-instillation is so minimal compared to everyday regular clinical practice amounts of fluorescein dye used on the eye that it was unlikely to cause the adverse effects of sequential staining or confound the results.

8. The subject is asked to undertake three natural blinks (i.e., not rapid or "squeeze" blinks) and then to hold the eyelids open while looking at one spot. The first sign of break up (dark spot or change) is recorded to the nearest tenth of a second. Following the first measurement a twenty to thirty second rest period of eye closure is allotted for the patient to re-establish tear stability before measuring the other eye. A minimum of three measurements are taken for each eye with the rest period between each measurement, alternating between eyes. If a measurement is deemed unreliable (i.e., if a subject did not follow instructions, observation is uncertain, or if the tear film contains too much debris) a fourth measurement is taken and the unreliable value is recorded. The mean of the three TBUT measurements, not including the unreliable measurement, is also recorded for each eye.

Corneal Staining

- The slit lamp used to view the corneal staining is set at maximum illumination on cobalt blue filter, 14 mm round beam, and medium (16x) magnification. Additionally, a yellow #12, 55mm Tiffen filter is used to maximize visibility of the fluorescein staining.
- 2. Corneal staining is evaluated immediately following TBUT without additional instillation of NaFl solution. Observations are made shortly after TBUT evaluation because the fluorescein diffuses rapidly into the tissue.^{55,59,60} If not enough dye is present to evaluate fluorescein staining due to quick lacrimal drainage, study

procedures allow for an additional amount of fluorescein to be instilled prior to grading.

- 3. National Eye Institute (NEI) systems. The NEI scheme has an integer severity scale of 0 to 3 for each of five corneal sectors for a total corneal scale of 15.⁵⁴⁻⁵⁶ For NEI schemes, the scales are outlined with illustrated grading panels (Appendix III, Case report form). The scales assess the area, but not depth, of punctate staining, which increase on a log scale, with the highest number being the most staining and most severe. When the examiner graded the level of staining, the grading panels were readily visible and referenced during the evaluation.
- 4. Corneal staining evaluation is quantified using the Ocular Staining Score (OSS) (only at screening and baseline).⁶¹ Punctate epithelial erosions (PEE) that stain with fluorescein are counted, and scored. If there are no PEE, the score is 0. If 1-5 PEE are seen, the corneal score is 1 (Appendix IV); 6-10 PEE are scored as 2; and >30 PEE are scored as 3. An additional point is added if 1) PEE occurred in the central 4mm diameter portion of the cornea; 2) one or more filaments are seen anywhere on the cornea; or 3) one or more patches of confluent staining, including linear stains, are found anywhere on the cornea. The total fluorescein score for the cornea (the PEE grade plus any extra points for modifiers) is noted in the central square of the SICCA ocular staining score form (Appendix IV). The maximum possible score for each cornea is 6.

Conjunctival Staining

9. A sterile lissamine green strip is wetted with a drop of sterile saline solution. The dye is applied on the superior bulbar conjunctiva on the right eye, followed by the

left eye. The subject is then moved back into the slit lamp headrest, and analysis is performed immediately after the dye was applied. The slit lamp biomicroscope is immediately utilized to visualize the bulbar conjunctiva with moderate high illumination of white light, wide beam (~14mm round), and 16x magnification. The subject is asked to look opposite to the side of the conjunctiva being visualized in order to reveal more of the conjunctiva clearly.

10. Conjunctival staining evaluation is quantified using the OSS and NEI systems. In the OSS, grade 0 is defined as 0-9 dots of lissamine green staining of the interpalpebral bulbar conjunctiva (nasal and temporal conjunctivae graded separately); grade 1 is defined as the presence of 10 to 32 dots; grade 2 as 33 to 100; and grade 3 > 100 dots. Because of the difficulty of counting individual dots in a moving eye at the slit lamp, any area of confluent staining >=4 mm² is considered to be >100 dots. Nasal and temporal areas of the conjunctiva are graded separately with a maximum score of three for each area or a total maximum score of 6 for each eye. The total OSS for each eye is the summation of the fluorescein score for the cornea and the lissamine green scores for the nasal and temporal bulbar conjunctiva.⁶¹ The NEI scheme has an integer severity scale of 0 to 3 for each of six conjunctival sections (three sections each nasal and temporal sides) for a total corneal scale of 0-18.54-56 For both schemes, the scales are outlined with illustrated grading panels(Appendix III Case Report form). The scales assess the area, but not depth, of punctate staining, which increase on a log scale, with the highest number being the most staining and most severe. When the examiner grades the level of staining, the grading panels are readily visible and referenced during the evaluation.

Meibum Gland Excreta Grading

1. Procedure: Gland expression is assessed using a slit-lamp biomicroscope at medium (16x) magnification, moderate white light and a wide, 14 mm diffuse beam. A constant pressure device, the Meibomian Gland Evaluator (MGE) developed by Blackie and Korb in 2008⁵⁸ is utilized, allowing for standardized and consistent pressure. Prior to gland expression, a Q-tip wetted with non-preserved saline will be used to gently wipe the lid margin to remove any debris.⁵⁸ First, the subject is informed that they will feel a tickling sensation on the eyelid margin as it gets wiped with the Q-tip, and the pressure exerted by the MGE is demonstrated on the subject's hand. The subject is instructed to look up and away from the Q-tip or the MGE for the duration of the procedure. To clean the eyelid margin, the investigator gently pulled the skin down by placing the index finger over the edge of the orbital margin in order to prevent any accidental expression of the meibomian glands. Once the eyelid margin is revealed, it is gently wiped with a moistened Qtip. The investigator held the MGE 1-2 inches from the tip and applied it to the subject's lower eyelid at the base of the lash line to locally push the tarsal plate of the lower eyelid against the globe to express the meibomian glands. As the MGE is applied, it is angled down and the pressure was held for 10 - 15 seconds, watching for oil excretion from the glands to evaluate both the secretion quality and number of glands expressing oil. Expression proceeds targeting approximately 8 glands at the center of lower eyelid. Expression grade and secretion quality are graded individually. The procedure is repeated for each eye.

2. Grading Scales: Grading is based on the average appearance of the center lower eyelid region of a single eye. The Bron scale, initially proposed in 1991,⁶² is utilized for Meibomian secretion quality, which uses the color and viscosity of the excreta observed graded on a scale of 0 to 3, as described in Table 6.^{6,57}

11.

Grade	Meibum	Meibum Quality Description
	Quality	
Grade 0	Clear	Normal
Grade 1	Cloudy	Diffusely turbid fluid secretions
Grade 2	Granular	Usually turbid fluid secretions, but contains particulate matter. The color of these secretions varies from whitish to yellow.
Grade 3	Inspissated	A semisolid plug or a substance of toothpaste- like consistency; may be extruded as a plug or curled thread. Expression is usually delayed or requires extra pressure. The material contains keratinized epithelial cells.

Table 6: "Bron Scale" Meibomian Gland Expression Grading^{6,57}

12.

Schirmer 1 Test

13. The Schirmer test without anesthetic is performed with the subject's eyes gently closed. The subject is told to look upward and blink normally while the strip is placed in the right eye then the left. The Schirmer strips are placed at the junction of the middle and lateral one-third of the lower eyelid. After five minutes the strips are removed, and the amount of wetting is recorded in millimeters. While in the subject's eye, the strip is monitored carefully; if after 2 minutes no wetting is

observed the strip is repositioned for the remainder of the five minutes, and the action is recorded. Due to the discomfort during the procedure, if a subject wets a minimum of 10mm of both strips in less than five minutes, the strips are removed. Care is taken to avoid contaminating the test strip with skin oil from the examiner.^{46,59}

Meibography with LipiView II (TearScience, Morrisville, North Carolina, USA)

- The LipiView II (Tear Science, Morrisville, North Carolina, USA) instrument is used to assess the area of Meibomian gland loss. Images of the subject's eyes are saved on a password protected LipiView instrument consistent with HIPAA. The images are transferred to a flash drive then to a secure research computer for analysis using Image J software for percent Meibomian glands remaining.

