In contradistinction, the studies by Worda et al⁸ and Connor et al.^{16-21,26,31} have examined topical eyelid androgen application with generally favorable effects on tear film parameters and also a good safety profile. However, the eyelid application studies were not consistent in the subject type (e.g., both males and females were not uniformly enrolled), the androgen status and serum levels were not assessed prior to, or following androgen application and the studies were only published as peer-reviewed abstracts and mostly were done in one laboratory. This prospective randomized, controlled double masked study aims to evaluate the efficacy and safety of topical transdermal application to the eyelids of low dosage androgen in a population of patients with evaporative dry eye associated with meibomian gland dystrophy and aqueous tear deficient dry eye.

Methods

Study objective

To evaluate the safety and efficacy of an FDA-approved androgen nasal supplement (Natesto, Acerus Pharmaceuticals Corporation, 4.5% gel concentration) in males and females with dry eye of either aqueous tear deficiency or evaporative subtype.

Clinical hypothesis

- Natesto applied to upper and lower eyelid skin is more effective than placebo as measured by fluorescein tear breakup time (TBUT) and mean scores for meibomian secretion quality at 4 weeks and overall ocular comfort at 8 weeks.
- Natesto has an acceptable safety profile in ocular structures and general systemic system.

Statistical Hypotheses:

H₀: There is no difference in change from baseline to week four for either fluorescein breakup time (TBUT) or meibomian secretion score (0 - 24 scale) between the test and placebo-treated sample.

 H_A : There is a difference in the change from baseline to week four for either fluorescein breakup time (TBUT) or meibomian secretion score (0 – 24 scale) between the test and placebo-treated sample

Overall study design

Structure

We propose a randomized controlled trial (RCT) of one month duration dosing BID with

an FDA-approved androgen nasal supplement (Natesto, Acerus Pharmaceuticals

Corporation, 4.5% gel concentration) in males and females with dry eye of either aqueous tear deficiency or evaporative subtype.

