- In this present investigation the principal outcome measures, fluorescein TBUT (using 2.0 microliters of 1.0% sodium fluorescein) and the system for meibomian gland secretion (0-24 scale) are recommended by the MGD workshop and DEWS II diagnostic committees.⁴ Table 2 shows the sample size estimation with two arm parallel design, comparing the change from baseline in FTBUT in each arm with a two sample t-test continuous data, clinically meaningful change of 2.5 seconds with Standard Deviation (SD) following treatment of 2.5 seconds. The results are as follow:
- 2-Sample t Test
- Testing mean $1 = \text{mean } 2 \text{ (versus } \neq \text{)}$
- Calculating power for mean 1 = mean 2 + difference
- $\alpha = 0.05$
- Assumed standard deviation = 2.5

Table 2: Sample size estimation

_	Difference	Sample Size	Target Power	Actual Power
	2.0	26	0.8	0.807487
	2.5	17	0.8	0.807037
	3.0	12	0.8	0.802079
	3.5	10	0.8	0.841306

4.0

0.8

0.844793

- 2.
- 3. With the actual power of 0.807, total of 34 subjects with seventeen (17) subjects per arm will be recruited for this study.

8

Randomization method

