Appendix III: Dry Eye Classification Criteria and Appendix V: Staging the Severity of MGD-Related Ocular Surface Disease

17. General statistical methods and types of analyses

- Comparisons, ANOVA, meibomian secretion scores, meibomian gland dropouts, OSDI
- The primary visit is week 4 and primary efficacy variables are the FTBUT and quality of meibomian secretions
- A two-sided test with p-value less than or equal to 0.05 will be considered as statistically significant.
- 18. Comparisons between pairs of treatment groups will be done with Cochran-Mantel Haenszel (CMH) tests, stratified by the ocular discomfort strata. Within Strata comparisons will be done with Wilcoxon rank-sum tests for both ordinal and continuous variables. For nominal variables, within strata comparisons will be done with Pearson's chi-square or Fisher's exact tests.
- 19. Exploratory pharmacokinetics data analysis
- Summary statistics of testosterone, dihydrosterosterone, and 3-alphaandrostanediol glucuronide serum concentrations will be calculated. The relationships between treatment time and gender will be examined.

Confidentiality

The identity of the subjects will be treated as confidential. The results of the study, including any other data, may be published for scientific purposes but will not reveal the name of the subject or include any identifiable references to the subject. Although

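### Two week-4 primaries, either of which rejects the null at an unadjusted 0.05, put the false-positive rate above 5% (up to 9.75%)

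*Combined protocol and SAP*

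**What the plan says.** Under Statistical Hypotheses, the null is "There is no difference in change from baseline to week four for either fluorescein breakup time (TBUT) or meibomian secretion score" and the alternative is "There is a difference in the change from baseline to week four for either fluorescein breakup time (TBUT) or meibomian secretion score". The list of efficacy measures under Evaluation criteria puts both variables under Primary. The section on general statistical methods (item 17) confirms this: "The primary visit is week 4 and primary efficacy variables are the FTBUT and quality of meibomian secretions". The same item gives the only significance criterion: "A two-sided test with p-value less than or equal to 0.05 will be considered as statistically significant".

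Two other places bear on the rule. The Clinical hypothesis section links the endpoints differently, claiming superiority on "fluorescein tear breakup time (TBUT) and mean scores for meibomian secretion quality at 4 weeks and overall ocular comfort at 8 weeks". The Sample size estimation section works from FTBUT only, "comparing the change from baseline in FTBUT in each arm with a two sample t-test continuous data", and concludes: "With the actual power of 0.807, total of 34 subjects with seventeen (17) subjects per arm will be recruited for this study". It gives no effect size or power for the secretion score.

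**The concern.** The null says that neither variable differs and the alternative says that at least one does. They are complements, so a significant result on one primary is enough to reject. That gives two chances of a positive primary result, and the text provided sets 0.05 as the bar for each without controlling the overall error.

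Two things are at stake. First, a gel with no effect on either primary would be declared effective more often than the nominal 5%. Second, the sample size rests on a power figure for one endpoint at full alpha, so it does not show what the trial can detect once the error is controlled. The wording of the clinical hypothesis adds doubt about which rule applies, and that doubt could be resolved after the data are seen.

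**Working it through.** **Inputs.** From the protocol: two primaries at one visit; two-sided 0.05; FTBUT difference 2.5 s, SD 2.5 s, 17 per arm, two-sample t-test. Assumed: the correlation r between the two endpoints, which the documents do not give. General Procedures has one eye per subject analysed, so both endpoints come from the same eye and some correlation is plausible. A range is shown.

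**Step 1: reproduce the plan's power.** Noncentrality = (2.5/2.5) / √(2/17) = √8.5 = 2.915, with 2 × 17 − 2 = 32 degrees of freedom. The two-sided 0.05 critical value is 2.037. Noncentral-t power is 0.8070, against 0.807037 in Table 2. The other four rows of Table 2 also reproduce to six decimals.

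**Step 2: false-positive rate of the either-endpoint rule.** With independent tests it is 1 − (1 − 0.05)² = 1 − 0.9025 = 0.0975. With correlated tests it is 1 − P(|Z1| < 1.96 and |Z2| < 1.96) for a bivariate normal pair with correlation r. Step 3 uses the same formula with each test at 0.025.

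| r | each test at 0.05 | each test at 0.025 |
|---|---|---|
| 0 | 9.75% | 4.94% |
| 0.3 | 9.5% | 4.84% |
| 0.5 | 9.1% | 4.65% |
| 0.7 | 8.3% | 4.30% |
| 0.9 | 7.0% | 3.62% |

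Negative correlations give the same values. The rate falls to 5% only as |r| approaches 1. Simulated t-tests at 17 per arm agree at the values checked: 9.7% at r = 0, 9.5% at 0.3, 9.1% at 0.5 and 7.8% at 0.8 (normal-theory value 7.81%). Without joint normality the bound is 0.05 + 0.05 = 10%.

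**Step 3: what control does.** The right-hand column is the chance of any false claim under Holm when both nulls are true, because Holm's first step tests the smaller p-value at 0.025. It stays below 5% throughout. A fixed sequence (FTBUT first, secretion only if FTBUT passes) gives 5.0%, because a false claim needs FTBUT to pass at 0.05.

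**Step 4: FTBUT power under each rule (t-test, difference 2.5 s, SD 2.5 s).**

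| evaluable per arm | alpha | power |
|---|---|---|
| 17 | 0.05 | 0.807 |
| 17 | 0.025 | 0.712 |
| 20 | 0.025 | 0.793 |
| 21 | 0.025 | 0.815 |

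The 0.712 is the floor under Holm, reached when secretion contributes nothing. Power rises towards 0.807 as the secretion effect grows, but that effect is not in the documents, so only the floor can be stated.

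**Step 5: dependence on the test.** These figures hold for a t-test. As an illustration, an unstratified Wilcoxon test on normal data with 17 per arm has power of about 0.78 to 0.79 at 0.05 and 0.67 to 0.68 at 0.025. The plan's stratified CMH test was not evaluated.

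**The case against.** The strongest reply is that the hypotheses are not a decision rule. The protocol never says how two p-values decide one null, and the clinical hypothesis joins the endpoints with *and*. If both primaries had to succeed, no alpha adjustment would be needed.

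Part of this stands. The two wordings do conflict, and requiring both would be a legitimate rule. Its cost is joint power, which could not exceed 0.807 on the plan's own t-test figure and cannot be computed without a secretion effect. But the clinical hypothesis sets no success criterion, and it adds ocular comfort at week 8, which is not a listed primary. The formal hypotheses are the operative text, and they say *either*.

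Three smaller points are fair. The 9.75% maximum depends on joint normality, and secretion is a bounded 0–24 score, so the assumption-free bound is 10%. The Wilcoxon figures match neither the plan's CMH test nor its within-strata use of Wilcoxon, so they are only illustrative. The 0.807 survives a fixed sequence only if a t-test on FTBUT is adopted.

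It can also be said that this is a small trial whose p-values will both be visible. That does not excuse the rule: the trial is randomised and double-masked, with formal hypotheses, a significance threshold and an efficacy objective.

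**Conclusion.** The concern holds and should be fixed before unmasking. Read literally, the plan allows a primary efficacy claim from either of two tests at an unadjusted 0.05. The false-positive rate is then 9.75% at zero correlation and 7.0% at 0.9 under joint normality, and never more than 10%. The stated 0.807 is correct for what it describes (FTBUT alone, t-test, 0.05, 17 evaluable per arm), but it is not the power of an error-controlled either-endpoint rule.

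The conclusion rests on the formal hypotheses being the decision rule and on the text provided, in which no multiplicity control was found. The exact inflation depends on a correlation that the documents do not give; its existence does not, short of perfect correlation.

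**What to change.** State one error-controlled rule in Statistical Hypotheses and in item 17, and bring the clinical hypothesis into line with it. Two options serve:

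- **Holm, keeping the either-endpoint claim.** Test the smaller p-value at 0.025 and, if it passes, the other at 0.05. Report FTBUT power at 17 evaluable per arm as 0.71, the worst case by t-test. This is below the 0.80 target. Restoring 0.80 at alpha 0.025 would take 21 evaluable per arm, which is 42 in all and 42 − 34 = 8 more.
- **Fixed sequence.** Test FTBUT first at 0.05, then secretion at 0.05 only if FTBUT passes. This keeps the t-test power of 0.807 at 34 evaluable subjects. The cost is that secretion cannot be claimed if FTBUT fails.

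Under either option, name the primary test for each endpoint and state power for that test. Item 17 has only a fragment, "Comparisons, ANOVA, meibomian secretion scores, meibomian gland dropouts, OSDI", and item 18 adds stratified CMH and within-strata Wilcoxon tests; none is assigned to a primary. If ANOVA means a one-way comparison of the two arms, it is the t-test of the sample size section, and the plan should say so.

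The change is to wording only and needs no extra patients, unless the sponsor chooses Holm and wants 0.80 in the worst case.

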One aspect of local, transdermal application of testosterone to the eyelids is the affected surface area. The upper and lower eyelid surface area is around 8% of one adult handprint (the average surface area of both sides upper and lower eyelid is 14.2 cm² (π * 1.5cm*1.5cm*2: the area of upper and lower eyelid is close to a circle with diameter of the length of horizontal eyelid fissure around 3.0 cm. ⁴⁰) compared to one handprint 180cm² (1% of body surface area BSA 1.8m²)). The total dosage needed to cover both upper and lower eyelid surfaces is much lower than the systemic application of androgen in the study of Supalaset¹⁰ (98 cm²; 7cm*14cm: the area the author used to apply androgen cream). The eyelid application is thus a small, and likely safe dosage relative to systemic safety.

There is very little reported data concerning serum testosterone levels following eyelid application. Worda et al.,⁸ in one subject who was testosterone deficient, applied 3.0% testosterone cream three times daily and had no change in serum testosterone levels following 2.5 months of drug application. [name] has conducted several studies^{16-21,24,26,31,41} of eyelid testosterone cream application but has not surveyed the serum testosterone changes that might result.

In collaboration with [name], of the College of Pharmacy at MBKU, we have examined the likely systemic absorption of androgen applied to the upper and lower eyelids BID in the dosage form currently FDA approved for androgen insufficiency (Natesto gel, 11 mg each single application for two eyelids or 22 mg per day total for two

applications to the eyelids per day). This simulation and report is attached as Appendix I (Simulation report, v3, [name], 12-6-21).

The assumption for the simulation was that the amount of gel necessary for one eyelid application was the size of a pea ([name], personal communication; email of 11-1-21) which [name] measured to be approximately 0.122 grams. This represents one pump of the Natesto dispenser or 5.5 mg of testosterone delivered.⁴² Applied to both eyelids at one application, this represents 11 mg total for a single application.

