The test formulation will be marketed Natesto gel, containing 5.5 mg testosterone per pump (17 β -Hydroxyandrost-4-en-3-one; inactive ingredients are castor oil, oleoyl polyoxylglycerides and colloidal silicone dioxide; Natesto package insert). The placebo is the exact same formulation without 17 β -Hydroxyandrost-4-en-3-one. The drug and placebo will be delivered to and dispensed by Caduceus Medical group in Yorba Linda for MBKU's study use.

Dosage regimen

One dose per eyelid of masked gel, which is one pump from the dispenser, represents 5.5 mg for each eyelid, will be applied on the surface of upper and lower eyelid skin each eye twice per day (separated by 8 hours) for a total daily dose of 22mg.

Duration

2-week screening period; 4-week masked treatment phase, 8-week washout phase.

Overall study duration 14 weeks

Visit schedule (see Table 4 and 5)

- Visit 1: Screening visit (Day -14)
- Visit 2: Baseline (Day 0) : the drug (placebo) is prescribed and dispensed.
 Instructions are given on how to properly apply the drug. Subjects are instructed to keep the container even if the drug is finished. All containers need to be checked in the following two visits (visit 3 & 4)
- Visit 2a: serum blood draw for baseline total testosterone level, hematocrit, lipid panel, PSA for men only at clinical laboratory

- Visit 3: Two-week visit: check the drug (placebo) to see if supplement needed.
 Empty containers need to be collected.
- Visit 4: Week 4: the drug (placebo) is discontinued. All dispensed containers need to be collected.
- Visit 4a: serum blood draw for treatment period total testosterone level at clinical laboratory (must be in AM, and must be within two hours of application)
- Visit 5: Week 8: 4-weeks washout phase follow up
- Visit 6: Week 12: 8-week washout phase follow up

Evaluation criteria

Efficacy measures

Primary

- Fluorescein tear breakup time (FTBUT)
- MGD secretion grade (0-24 scale)

Secondary:

- 1. Schein Questionnaire and Ocular Surface Disease Index (OSDI)
- Corneal and conjunctival staining as per the Oxford and National Eye Institute (NEI) schemes
- Tear Meniscus Height (TMH) utilizing Keratography 5M (K5M Oculus, Inc Arlington,WA)
- 4. Eyelid signs grading of orifice metaplasia, vascularity, plugged orifice, lid margin irregularity, ridging between orifices, and antero-posterior orifice displacement
- 5. Meiboscore utilizing K5M
- 6. Schirmer I test without anesthetic

Exploratory:

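### The dosing sentence can be read per eye (22 mg/day) or per lid (44 mg/day), and the only simulated testosterone rise in the protocol body is for 11 mg once daily, half the stated daily total

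*Combined protocol and SAP*

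**What the plan says.** **Dosing.** The Dosage regimen section reads: "One dose per eyelid of masked gel, which is one pump from the dispenser, represents 5.5 mg for each eyelid". The same sentence says that the gel "will be applied on the surface of upper and lower eyelid skin each eye twice per day (separated by 8 hours" and ends "for a total daily dose of 22mg". At Visit 2 in the Visit schedule, "Instructions are given on how to properly apply the drug". The text of those instructions is not part of the documents.

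**The word in the introduction.** The paragraphs on eyelid application and the simulation, just before Research Rationale, use the term in two senses. Where the treated area is compared with a systemic study, the text speaks of "both upper and lower eyelid surfaces", meaning single lids. Where the amount of gel is worked out, it says "Applied to both eyelids at one application, this represents 11 mg total for a single application". There each eyelid takes one 5.5 mg pump, so the two eyelids are two eyes. The introduction also gives 22 mg per day for two such applications.

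**Exposure.** The introduction states that "we have examined the likely systemic absorption of androgen applied to the upper and lower eyelids BID" and refers to Appendix I, a separate document that was not available here. The result it then quotes is for one application a day to upper and lower lids on both sides, 11 mg in all. The mean rise in total testosterone is about 0.15 to 0.18 ng/ml, after single or 30-day use. This one figure, not split by sex, is set against reference ranges of 2.54-8.90 ng/ml for men and 0.12-0.58 ng/ml for women. The text concludes that the rise could double the lower limit for women while possibly leaving them in range. It adds that virilization in women, and the effects of twice-daily use, are not yet known.

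**The concern.** The dosing sentence is the operative instruction. It names upper and lower lids of each eye and assigns a pump to each eyelid, so a reader can count four lids. A participant counts pumps, not milligrams. If the per-lid words reached the Visit 2 instructions without the total, use could be twice what the protocol states, in a testosterone trial that enrols women.

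The second part concerns what the protocol body offers as reassurance for women. Its one quantitative statement rests on half the daily amount that the protocol specifies. The first scheduled on-treatment serum level is at Week 4, when dosing stops, so no earlier scheduled measurement would show how far exposure differs from the quoted figure.

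**Working it through.** **Inputs.** From Dosage regimen: 5.5 mg per pump, one pump per eyelid, two applications a day, 22 mg/day stated. From the introduction: 0.122 g of 4.5% gel per eyelid application, 11 mg per application session, mean rise 0.15-0.18 ng/ml for 11 mg once daily, female range 0.12-0.58 ng/ml.

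**1. Pump content.** 0.122 g x 4.5% = 5.49 mg, which agrees with 5.5 mg.

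**2. Daily total.** mg/day = 5.5 x dosing units per session x 2 sessions.
- Unit is one eye's lid pair (2 units): 5.5 x 2 = 11 mg per session; 11 x 2 = 22 mg/day. This reproduces both stated figures. It takes 2 x 2 = 4 pumps a day.
- Unit is a single lid (4 units): 5.5 x 4 = 22 mg per session; 22 x 2 = 44 mg/day, or 4 x 2 = 8 pumps a day.
- Ratio: 44 / 22 = 2.

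**3. Regimen behind the quoted rise.** 11 mg once daily against 22 mg/day: 11 / 22 = 50%.

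**4. The plan's remark for women, at the once-daily rise.**
- From the lower limit: 0.12 + 0.15 = 0.27 and 0.12 + 0.18 = 0.30 ng/ml, which is 2.25 to 2.5 times 0.12 and inside the range. The hedged remark is reproduced.
- Baseline above which the upper limit is passed: 0.58 - 0.18 = 0.40 to 0.58 - 0.15 = 0.43 ng/ml.

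**5. Twice-daily use.** The documents give no figure, so this step is an assumption with a range.
- No further increase: rise 0.15-0.18 ng/ml, threshold baseline 0.40-0.43 ng/ml.
- Rise fully proportional to daily dose: 2 x 0.15 = 0.30 to 2 x 0.18 = 0.36 ng/ml, threshold baseline 0.58 - 0.36 = 0.22 to 0.58 - 0.30 = 0.28 ng/ml.
- Overall: rise 0.15-0.36 ng/ml, threshold baseline 0.22-0.43 ng/ml.
- A woman at the lower limit stays inside even at the top of this range: 0.12 + 0.36 = 0.48 ng/ml.

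The position within this range depends partly on whether 0.15-0.18 is a peak or an average, which the text does not say. That single and 30-day once-daily use give about the same figure suggests little build-up at that schedule. It does not settle two applications 8 hours apart.

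**The case against.** The documents already fix the intended meaning. The dosing sentence carries its own total, and the introduction repeats 11 mg per application and 22 mg per day. A full copy of the sentence would take the 22 mg with it. On exposure, the text openly labels its once-daily basis, says that twice-daily effects are unknown, and claims only that women may remain in range. It also says that twice-daily absorption was examined, so Appendix I may hold the missing figure.

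Most of this stands, and it makes the point minor. What remains is that the operative sentence does not define its unit, that the introduction uses the word in both senses, and that the protocol body draws its statement about women from a regimen other than the one it specifies.

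Some stronger readings are tempting but not supported:
- A reader might infer that 22 mg is an error, or that participants will receive 44 mg. Neither follows: the total reproduces per eye, and the Visit 2 instructions are not available.
- A reader might infer that twice-daily exposure was never simulated. The appendix has not been seen, so this cannot be said.
- A reader might infer that women will leave the normal range, or how many will. The documents give no distribution of baselines, and low baselines stay inside throughout.
- A reader might treat 0.15-0.18 as build-up from single to repeated use and derive a ceiling for the twice-daily peak. The text gives that range for both kinds of use and describes no absorption model, so it supports no such ceiling.
- The containers are checked at Visits 3 and 4 without a stated expected use. That is absent detail, not a contradiction.

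**Conclusion.** The point holds as a matter of wording and reporting; severity is minor. The dosing sentence admits two readings a factor of two apart, 22 or 44 mg/day, and only the first agrees with the stated total and the introduction. The rise quoted in the protocol body, and the normal-range remark for women, belong to 50% of the specified daily amount. Even on that basis the remark fails for baselines above 0.40-0.43 ng/ml. For the planned regimen the corresponding threshold lies somewhere in 0.22-0.43 ng/ml. That range rests on the assumption that the rise is between unchanged and proportional to daily dose, and on applying one mean rise, not split by sex, to women. The first part is certain from the text. The practical weight of the second depends on what Appendix I contains.

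**What to change.** Reconcile the introduction and the Dosage regimen section by defining the dosing unit once, per eye or per lid, so that pumps, applications per day and mg/day agree. Use the same words in the Visit 2 subject instructions. Which regimen is intended is for the sponsor to state; none is recommended here.

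Tie the expected rise, and the normal-range statement for women, to the planned twice-daily regimen. Quote that result from Appendix I or, if the appendix lacks it, run the existing simulation for that schedule. Say whether the figure is a peak or an average.

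The cost is a few lines of protocol and instruction text, and at most one further run of an existing simulation. Design, endpoints and sample size are unaffected.
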